A study performed by Choi et al. evaluated the use of [¹⁸F] FDG PET/CT in assessing response to neoadjuvant therapy in PDAC. This study showed that a decrease of more than 50% of standardised uptake value (SUV) on PET-CT was strongly predictive of R0 resection (19).

Ultimately, there is very little literature about the use of PET-CT scan for this indication. This raises the interest in evaluating [⁶⁸Ga] FAPI PET/CT as a marker of tumour response to neoadjuvant therapy in PDAC.

3. Aims/Objectives

The primary objective of this study is to assess whether [⁶⁸Ga] FAPI PET/CT provides clinical benefit in patients with resectable or borderline resectable PDAC who have been referred for neoadjuvant chemotherapy.

The specific aims of this study are as follows:

1. To compare the SUVmax of [⁶⁸Ga] FAPI PET/CT to [¹⁸F] FDG PET/CT in patients diagnosed with resectable or borderline resectable PDAC pre- and post-neoadjuvant chemotherapy.
2. To assess the percentage of fibroblast activation protein (FAP) expression in the pre-treatment biopsy specimen and the resected specimen and correlate this with [⁶⁸Ga] FAPI PET/CT SUVmax results pre- and post-neoadjuvant chemotherapy.
3. To assess the change in SUVmax on [⁶⁸Ga] FAPI PET/CT post neoadjuvant chemotherapy and correlate it with tumour response to chemotherapy determined on contrast enhanced CT scan and the resection specimen.

4. Hypotheses

For patients with potentially resectable PDAC this study sets out to prove that:

1. [⁶⁸Ga] FAPI PET/CT will be superior to [¹⁸F] FDG PET/CT in assessing tumour burden and its response to neoadjuvant chemotherapy.
2. Higher FAP expression in the tumour stroma will result in higher FAPI tracer uptake and is associated with a poorer response to neoadjuvant chemotherapy.
3. The change in SUVmax on [⁶⁸Ga] FAPI PET/CT following chemotherapy will correlate with response to treatment observed on contrast enhanced CT and pathological specimens. This correlation will be stronger than it is [¹⁸F] FDG PET/CT.

5. Methods

a. Study Design

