This study is a single-centre, prospective study evaluating the utility and clinical benefit of [⁶⁸Ga] FAPI PET/CT in 20 patients deemed to have resectable or borderline resectable PDAC on initial clinical evaluation and are considered suitable for neoadjuvant chemotherapy with FOLFIRINOX. The FOLFIRINOX regimen is a currently accepted standard of care chemotherapy for resectable or borderline resectable PDAC. Patients will undergo FDG-PET/CT which is also accepted care in the work up of a patient with potentially resectable pancreatic cancer. Because [⁶⁸Ga] FAPI PET/CT remains an experimental imaging modality, any findings on [⁶⁸Ga] FAPI PET/CT that could alter patients' clinical decision making will be confirmed through biopsy or another established imaging modality and discussed at the HPB MDT meeting.

b. Study Site

This study will take place at Princess Alexandra Hospital (PAH), Woolloongabba, QLD, Australia. Metro South Health will be the primary sponsor for this study. The [⁶⁸Ga] FAPI isotope will be obtained from the Radiology department at the Royal Brisbane and Women's Hospital and couriered to PAH Radiology department in accordance with the "Code for the Safe Transport of Radioactive Material' guidelines.

Should there not be adequate recruitment of patients at PAH, feasibility to extend this study to include the Royal Brisbane and Women's Hospital will be considered.

c. Study Population

i. Sample Size

This study aims to recruit approximately 20 patients who have been referred to any hepato-pancreato-biliary (HPB) surgeon or medical oncologist within the PAH catchment. Any patient who fulfils the inclusion criteria, and is willing to participate in the study, will be included.

ii. Inclusion Criteria

- Age > 18 years
- Able to give informed consent
- Histological specimen from the primary pancreatic lesion confirming the diagnosis of PDAC.
- Patients need to have either a resectable or borderline resectable pancreatic lesion after imaging review at the HPB multidisciplinary (MDT) meeting
- No metastatic disease
- Eastern Cooperative Oncology Group performance status ≤ 1
- No contraindications to neoadjuvant chemotherapy.

iii. Exclusion Criteria

- Patients not medically fit for peri-operative chemotherapy with FOLFIRINOX or surgery
- Patients with known or suspected metastatic disease
- Pregnant or breastfeeding patients (if a female patient is pre-menopausal, she will require a negative urine pregnancy test prior to enrolment)

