All patient data will be de-identified, and laboratory staff will not have access to clinical information or re-identifiable patient data. Re-identifiable patient data will be analysed within the PAH Medical Oncology department. Tissue samples will only be collected as part of a participant's usual management. No invasive tissue sampling will take place solely for the purpose of the study.

Following repeat PET/CT scanning, the patient's response to chemotherapy will be discussed at the HPB MDT meeting and evaluated for surgery. If still deemed resectable, the patient will proceed to surgery. Resection specimens will undergo routine histological evaluation as per standard guidelines. After diagnostic requirements have been completed, IHC for FAP expression will be performed at TRI histology core facility as per the above procedure.

If the patient is deemed unresectable, the patient will be evaluated, and treatment options will be offered as per the standard of care for metastatic or unresectable PDAC.

d. Study Measures

A qualified nuclear medicine physician will interpret the results from the [¹⁸F] FDG and [⁶⁸ Ga] FAPI PET/CTs. The following measures will be obtained from the images produced:

- SUVmax of [⁶⁸ Ga] FAPI uptake in tumour deposits pre-chemotherapy at 60 minutes post-radio-isotope injection
- SUVmax of [¹⁸F] FDG uptake in tumour deposits pre-chemotherapy at 60 minutes post-radio-isotope injection
- SUVmax of [⁶⁸ Ga] FAPI and [¹⁸F] FDG post four cycles of chemotherapy at 60 minutes post-radio-isotope injection.

The response to chemotherapy will be evaluated at the HPB MDT meeting, where decisions about surgical resection are determined. Any discussions regarding change of management will be discussed with the treating clinician. No changes in management will be based on [⁶⁸Ga] FAPI-PET/CT results. These decisions will be made based on the results of standard of care investigations.

Histological analysis of the pre-treatment biopsy specimen and the resected specimen will be performed by a qualified pathologist at PAH. IHC for FAP staining will be performed on the specimens after routine histological evaluation has been completed according to standard protocols.

Measures from each tissue sample will include:

- Proportion of stromal cells stained.
- Intensity of staining for stromal cells.
- Proportion of neoplastic cells stained.
- Intensity of staining for neoplastic cells.

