- Dominant pattern of staining (i.e., stromal cells only, neoplastic cells only, or mixed).

7. Data Analysis and Statistical Methods

Descriptive statistics (frequencies and percentages) will be reported for categorical variables and interquartile range (IQR) will be reported for continuous variables.

We will compare the SUVmax response using a paired t-test or Wilcoxon rank-sum test for the following:

- [⁶⁸Ga] FAPI PET/CT and [¹⁸F] FDG PET/CT pre-chemotherapy
- [⁶⁸Ga] FAPI PET/CT pre- and post-chemotherapy
- [¹⁸F] FDG PET/CT pre- and post-chemotherapy

We will plot receiver operating characteristic (ROC) curves and calculate areas under the curve (AUCs) for each parameter to determine cut-points with optimal sensitivity and specificity. A two-sided P-value of <0.05 will be considered significant throughout.

For the patients' tissue analysis, we will perform linear regression, adjusting for potential confounders to determine if proportion and intensity of staining is related to SUVmax of primary pancreatic lesions. We will do this separately for both stromal and neoplastic expression. For each pattern of FAP expression (i.e., stromal cells only, neoplastic cells only, or mixed) we will determine median e SUVmax-p and IQR. We will compare groups using parametric or non-parametric tests depending on distribution of absolute SUVmax-p.

8. Data Management

a. Data Collection

Information required for this study will be collected directly from the participants and their medical records. Only the study investigators assigned to this research will have access to the patients' personal and medical information, pathology and initial imaging results and imaging data collected as part of the study.

b. Patient Confidentiality

Personal information and data collected will be treated in line with the Office of the Australian Information Commissioner's health privacy guidelines. In this study, data will be in re-identifiable form because data analysis and interpretation depend on patients' medical characteristics.

Participants in the study will have an identification code number allocated at enrolment. Patient data collected will be recorded under the participant's identification code. A code list linking the participant's identification number to their name will be kept by the Coordinating Principal Investigator in a password protected file in the Queensland Health secure server.

c. Data Security

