The FAPI molecule is a good therapeutic candidate because of its high uptake in pancreatic malignancies with negligible uptake in normal tissue. FAPI can therefore be used as an isotope to carry radioactive nuclides directly to the pancreatic tumour delivering a high dose of cytotoxic radiation and potentially overcome treatment resistance

Ultimately, this study will hopefully guide further research to bring about the clinical translation of this novel tracer. It will also allow our collaborative to establish FAPI manufacture locally, give our clinicians experience in the use of this PET tracer and enhance our track record in this research field to attract

future larger grants. Subsequent studies based off this study will only be undertaken once appropriate ethics and governance approvals have been sought.

12. Publication and Reporting

Data collected during this study is confidential, and no data identifying any participant will be published. The primary manuscript of this study will be presented to the academic community through posters and presentations at relevant forums. It will also be submitted to a suitable peer-review journal for consideration for publication. Participants will be given access to the manuscript at their request.

Should an incidental finding been discovered by [68Ga] FAPI PET/CT, it will be raised at the HPB MDT meeting and cross referenced with standard of care investigations. Decisions/ discussion points from the HPB MDT will be conveyed to the patient's treating clinician. No clinical decisions will be made from [68Ga] FAPI PET/CT alone. The patients treating clinician can then discuss further management of incidental findings with the patient.

13. References

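### The primary objective, clinical benefit of FAPI PET/CT, has no measure or analysis behind it, and no comparison is named primary although P<0.05 governs at least eight tests

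*Protocol*

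**What the plan says.** The Synopsis and Section 3 (Aims/Objectives) give one primary objective: to assess whether FAPI "PET/CT provides clinical benefit in patients with resectable or borderline resectable PDAC who have been referred for neoadjuvant chemotherapy". Section 5a (Study Design) repeats clinical benefit as the purpose of the study.

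Three specific aims follow: compare SUVmax between tracers, relate FAP expression to FAPI SUVmax, and relate the change in FAPI SUVmax to tumour response on CT and in the resected specimen. Section 6d (Study Measures) lists SUVmax for each tracer before and after chemotherapy and five staining features. It also says that response will be evaluated at the MDT.

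Three places deal with acting on FAPI findings:

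- Section 6d: "No changes in management will be based on [⁶⁸Ga] FAPI-PET/CT results", followed by "These decisions will be made based on the results of standard of care investigations".
- Section 5a: FAPI findings "that could alter patients' clinical decision making will be confirmed through biopsy or another established imaging modality and discussed at the HPB MDT meeting".
- Section 12 (Publication and Reporting), on incidental findings: "No clinical decisions will be made from [68Ga] FAPI PET/CT alone".

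Section 4 (Hypotheses) opens with "For patients with potentially resectable PDAC this study sets out to prove that" and lists three hypotheses. Section 7 says: "A two-sided P-value of <0.05 will be considered significant throughout". No aim, measure or test is called primary.

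**The concern.** A primary objective should lead to something that is recorded and analysed. Benefit to patients would have to appear as a patient outcome, or as a management decision that was better or different because of the FAPI scan. A higher SUVmax on one tracer, or a link between SUVmax and staining, shows neither. If the plan is followed exactly, the study finishes without an answer to its own primary question.

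The second strand concerns what may be claimed. A protocol that aims to prove three hypotheses, declares significance at 0.05 for every test and ranks none of them gives the reader no way to tell a confirmatory result from one of several that happened to cross the line. The 5% error rate applies to each test and not to the study's conclusions as a whole.

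**Working it through.** **1. Objective against measures.** The table sets each planned item beside what it can show.

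| Planned item | Where | What it informs |
|---|---|---|
| SUVmax, two tracers, two times | 6d | Uptake |
| Proportion, intensity and pattern of staining | 6d | FAP expression |
| Response at MDT, on CT, in specimen | 6d, Aim 3 | Response to chemotherapy |
| Three paired SUVmax contrasts | 7 | Uptake differences |
| ROC curves and AUCs | 7 | Cut-points |
| Staining regressions and pattern comparison | 7 | Expression against uptake |

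No row measures a patient outcome or management impact attributable to FAPI.

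**2. The three passages on management.** Section 6d excludes any change based on FAPI results. Section 5a sends findings that might alter decisions to confirmation and then to the MDT. Section 12 excludes decisions only when they rest on FAPI alone. Read literally, 6d is stricter than the other two. Under 5a and 12, a FAPI finding could lead to a confirmed finding and so to a changed plan. Neither 6d nor Section 7 counts such events.

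**3. Number of tests in Section 7.**

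- Paired SUVmax contrasts listed: 3.
- Staining coefficients: proportion and intensity, each for stromal and neoplastic expression, 2 × 2 = 4.
- Comparison across staining patterns: 1.
- Floor: 3 + 4 + 1 = **8**.
- Adding tests on AUCs for four SUVmax parameters (2 tracers × 2 times; an assumption, since the parameters are not listed): 8 + 4 = **12**.
- Splitting biopsy and resection specimens, no AUC tests: 3 + 8 + 2 = **13**.
- Both: 3 + 4 + 8 + 2 = **17**.

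Hypothesis 3 would add more, but Section 7 names no test for it, so none is counted.

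**4. Chance of at least one false positive.** With k independent tests, all null, each at 0.05, the chance is 1 − 0.95^k. The expected number of false positives is 0.05k.

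| k | 1 − 0.95^k | 0.05k |
|---|---|---|
| 8 | 33.7% | 0.40 |
| 12 | 46.0% | 0.60 |
| 13 | 48.7% | 0.65 |
| 17 | 58.2% | 0.85 |

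The tests share patients and SUVmax values, so independence is only a reference case. For k = 8 with all nulls true, the chance lies between 5% (tests perfectly dependent) and the Bonferroni bound of 8 × 0.05 = 40%.

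**5. Would adjustment serve instead?** The protocol gives no effect size, SD or power, so its figure of about 20 patients cannot be reproduced. Taking 20 complete pairs and a paired t-test, 80% power at two-sided 0.05 needs a standardised difference of 0.66. Bonferroni over 8 tests sets each at 0.05/8 = 0.00625. The detectable difference then rises to 0.89, and power at 0.66 falls to 47%. One primary analysis with the rest exploratory suits this sample better.

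**The case against.** **The aims give the objective its content.** Section 3 introduces Aims 1 to 3 as the specific aims of the study, so the objective may be broadly worded rather than empty. This stands in part. The aims are measurable, and response is collected. But none of them concerns benefit, so meeting all three would still leave the primary objective unanswered.

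**A reader might infer that benefit cannot occur at all,** because Section 6d bars management changes. The documents do not support that. Sections 5a and 12 leave the route through confirmation and the MDT. What holds is that the passages disagree and that no measure captures the route.

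**A reader might infer that a dozen or more tests are certain.** Section 7 fixes only eight. It calculates AUCs to set cut-points and states no test on them, and it does not say that biopsy and resection specimens are analysed separately. The higher counts are readings of the text.

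**A reader might infer that any single significant result would count as proof.** The protocol has no such rule. It lists three hypotheses, and the FDG comparison before and after chemotherapy would by itself prove none of them. The weakness is that nothing ranks the results.

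**The single arm is not decisive.** Every patient has both scans, so FAPI can be compared with FDG within patients.

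**The SAP may rank the tests.** It may, and the absence of a hierarchy alone would not be a finding. But the primary objective belongs to the protocol, a SAP cannot analyse what was not recorded, and the protocol itself fixes both the aim to prove and the uniform 0.05 rule.

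**Conclusion.** The point holds in this form. The stated primary objective has no measure and no analysis, so the plan as written cannot answer it. This rests on a direct reading of Sections 3, 5a, 6d and 7 and needs no calculation. Sections 5a, 6d and 12 conflict on what may follow from a FAPI finding and must be reconciled; this review takes no position on which should prevail.

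The multiplicity strand also holds, with its size depending on assumptions: at least 8 tests and up to about 17, and a chance of some false positive of about 34% to 58% if all are independent and null. Correlation between tests makes these figures illustrative. Whatever the count, significance at 0.05 in one unranked test does not support the word *prove*.

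**What to change.** 1. **Restate the primary objective** (Synopsis, Sections 3 and 5a) as something the study measures. For example: to estimate the association between percent change in FAPI SUVmax and tumour response. Name one response measure. The choice matters, because a pathological measure exists only for patients who reach resection.
2. **Name that estimate, with its 95% CI, as the single primary analysis** in Section 7. Make the FAPI-FDG difference in association secondary, since it is a separate estimand. Label all other p-values exploratory and limit the 0.05 rule accordingly.
3. **In Section 4, replace *prove* with *estimate*.**
4. **Reconcile Sections 5a, 6d and 12** on FAPI findings and management. That decision is for the sponsor and investigators.
5. **Only if clinical utility stays as an objective,** record the MDT's intended plan before and after the FAPI report, and report the proportion that differs with an exact 95% CI. What may be done with a FAPI finding is left to item 4.

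**Cost.** Items 1 to 4 change wording only; item 5 adds one form field. The claim becomes more modest, and the sample size limits precision either way. With 20 complete patients and a continuous response measure, an observed correlation of zero has a 95% CI of ±tanh(1.96/√17) = ±0.44. For item 5, 4 changed plans in 20 would give an exact interval of 6% to 44% (Clopper-Pearson 5.7% to 43.7%).

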Aims	
 1. To compare the SUVmax of [⁶⁸ Ga] FAPI PET/CT to [¹⁸F] FDG PET/CT in patients diagnosed with resectable or borderline resectable PDAC pre- and post-neoadjuvant chemotherapy. 2. To assess the percentage of fibroblast activation protein (FAP) expression in the pre-treatment biopsy specimen and the resected specimen and correlate this with [⁶⁸ Ga] FAPI PET/CT SUVmax results pre- and post-neoadjuvant chemotherapy. 3. To assess the change in SUVmax on [⁶⁸ Ga] FAPI PET/CT post neoadjuvant chemotherapy and correlate it with tumour response to chemotherapy determined on contrast enhanced CT scan and the resection specimen.
Research Questions	
 1. Is [⁶⁸ Ga] FAPI PET/CT more accurate than [¹⁸F] FDG PET/CT in determining tumour burden before and after neoadjuvant chemotherapy in patients with potentially resectable PDAC? 2. Does FAPI tracer uptake correlate with FAP expression on immunohistochemical evaluation of biopsy and resection specimens? Does higher FAP expression result in poorer response to chemotherapy? 3. Does the change in SUVmax on [⁶⁸ Ga] FAPI PET/CT following chemotherapy correlate with response to treatment in patients with potentially resectable PDAC? Is this correlation stronger than it is for [¹⁸F] FDG PET/CT?
Anticipated Outcomes	
 1. [⁶⁸ Ga] FAPI PET/CT will be superior to [¹⁸F] FDG PET/CT in assessing tumour burden and its response to neoadjuvant chemotherapy. 2. Higher FAP expression in the tumour stroma will result in higher FAPI tracer uptake and is associated with a poorer response to neoadjuvant chemotherapy. 3. The change in SUVmax on [⁶⁸ Ga] FAPI PET/CT following chemotherapy will correlate with response to treatment observed on contrast enhanced CT and pathological specimens. This correlation will be stronger than it is for [¹⁸F] FDG PET/CT.

Glossary of Abbreviations

CAFs	Cancer-associated fibroblasts
EUS	Endoscopic ultrasound
FAP	Fibroblast activation protein
FAP	Fibroblast activation protein
FAPI	Fibroblast activation protein inhibitor
FDG	Fluorodeoxyglucose
HIRF	Herston Imaging Research Facility
HPB	Hepato-pancreato-biliary
HREC	Human Research Ethics Committee
MDT	Multidisciplinary team meeting
MRCP	Magnetic resonance cholangiopancreatography
NHMRC	National Health and Medical Research Council
PAH	Princess Alexandra Hospital
PDAC	Pancreatic ductal adenocarcinoma
PET/CT	Positron emission tomography and computed tomography

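### Hypothesis 2 links FAP expression to chemotherapy response, but every stated FAP analysis relates staining only to SUVmax, so the response half has no analysis

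*Protocol*

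**What the plan says.** The response question appears three times in the Protocol. Hypothesis 2 in Section 4, among the statements the study intends to prove, says that higher stromal FAP expression raises tracer uptake and "is associated with a poorer response to neoadjuvant chemotherapy". The anticipated outcomes in the Synopsis repeat this. Research question 2 in the Synopsis asks: "Does higher FAP expression result in poorer response to chemotherapy".

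Aim 2 (Synopsis and Section 3) is narrower. It takes FAP expression in "the pre-treatment biopsy specimen and the resected specimen and correlate this with" the FAPI SUVmax before and after chemotherapy, and does not mention response.

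Section 7 plans two tissue analyses. The first is an adjusted linear regression "to determine if proportion and intensity of staining is related to SUVmax of primary pancreatic lesions", run separately for stromal and neoplastic expression. The second summarises SUVmax by dominant staining pattern: "We will compare groups using parametric or non-parametric tests depending on distribution of absolute SUVmax-p". Before these, and straight after the SUVmax comparisons, the section says it will plot ROC curves and "calculate areas under the curve (AUCs) for each parameter to determine cut-points with optimal sensitivity and specificity".

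Section 6d says where response is judged: "The response to chemotherapy will be evaluated at the HPB MDT meeting, where decisions about surgical resection are determined". Aim 3 adds contrast-enhanced CT and the resection specimen as sources of response information.

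**The concern.** A hypothesis listed for proof should have at least one analysis with its two variables on opposite sides. Hypothesis 2 needs FAP expression against response, and Section 7 gives only FAP expression against SUVmax. Followed as written, the study would report whether staining goes with uptake and would have no planned result on whether staining goes with response.

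The practical risk is that the gap is filled after the data are seen. FAP is measured on two specimens, in two cell compartments, as both proportion and intensity. Response could come from CT, the MDT or pathology. Section 7 applies a two-sided 0.05 threshold throughout. With that many possible pairings and none named, an analysis chosen late could be steered by its result.

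**Working it through.** No figure in the plan bears on this point, so the check matches each stated analysis to the two parts of Hypothesis 2: (a) FAP expression with FAPI uptake, and (b) FAP expression with response.

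| Stated analysis | Variables | Covers (a)? | Covers (b)? |
|---|---|---|---|
| Section 7, paired SUVmax comparisons | SUVmax between tracers before chemotherapy; SUVmax before and after within tracer | No FAP variable | No |
| Section 7, ROC curves | Parameters undefined; no reference outcome named | Not stated | Not stated |
| Section 7, linear regression | Staining proportion and intensity; SUVmax of the primary lesion | Yes | No |
| Section 7, staining-pattern groups | Dominant pattern; absolute SUVmax-p | Yes | No |

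Both analyses that name FAP staining use SUVmax as the other variable (2 of 2), and neither uses response (0 of 2). Aim 2 has the same pairing.

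Two ways of rescuing part (b) were considered.

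1. *SUVmax as a stand-in for response.* The tissue analyses use the SUVmax of the primary lesion, or its absolute value, and not its change over treatment. Even if the change were used, whether it tracks response is what Hypothesis 3 sets out to show, so it cannot be assumed in testing Hypothesis 2.
2. *The ROC sentence.* An ROC curve needs a binary outcome, and none is named. The sentence follows the SUVmax list and comes before the tissue paragraph. It is ambiguous, but it cannot be read as a stated analysis of FAP against response.

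If an analysis is added, the choice of specimen matters. Under Section 6c, biopsy FAP is measured on tissue taken before treatment. Resection FAP exists only for patients still judged resectable after four cycles, and is measured after treatment. Section 2 notes that tumour cells tend to disappear after chemotherapy while stromal fibrosis persists, so post-treatment staining may partly reflect the treatment itself. Biopsy FAP keeps the time order and does not depend on reaching surgery. Section 5c requires a histological specimen of the primary lesion for entry, so most patients should have biopsy tissue, though not necessarily enough left for staining.

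**The case against.** The strongest reply is that this is an omission, and that a statistical analysis plan not shown here may fill it. Section 7 does not claim to be exhaustive. It also names no test for Aim 3 and no comparison of the two tracers after chemotherapy, so it reads as an outline. On that view Section 7 matches Aim 2, and the mismatch lies between aims and hypotheses, which an edit of wording could settle.

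Part of this stands: deleting the response half is a legitimate repair. But the point is more than missing detail. The Protocol devotes a paragraph to the tissue analyses and describes how one half of Hypothesis 2 is tested, while the other half, asserted three times, is left out of both that paragraph and the aims.

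Three stronger readings are tempting, and the document does not support them.

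- A reader might infer that the study claims FAP *predicts* response. Hypothesis 2 states only an association; directional wording appears only in the Synopsis research question.
- A reader might infer that the plan would relate resection FAP to response and so reverse cause and effect. The Protocol proposes no such analysis. This is a risk only if the gap is later filled that way.
- A reader might treat patients found unresectable as the worst responders. The Protocol defines no ordered response scale, and that rule would mix resectability with response. Section 2 itself says that CT after neoadjuvant chemotherapy performs poorly in predicting margin-negative resectability.

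**Conclusion.** The point holds for the response half of Hypothesis 2, for the matching half of research question 2, and for the corresponding anticipated outcome. The uptake half is covered. The size of the defect is one of two halves of one hypothesis left without any stated analysis. It is not a numerical error, and a confidence interval computed for an assumed correlation would not measure it.

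The conclusion rests on reading the ROC sentence as not covering FAP against response, which its wording and position support. It also assumes that the Protocol's own list of FAP analyses is what would be carried out. The point is worth correcting because a stated question would otherwise end without a result or be answered by an analysis chosen afterwards. It does not affect the other hypotheses.

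**What to change.** Add one exploratory analysis to Section 7, reported with a 95% CI:

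- **Exposure:** stromal FAP expression in the pre-treatment biopsy, with the staining measure (proportion or intensity) named in advance. Resection FAP should not be the main exposure, because it is measured after treatment and only in patients who stayed resectable.
- **Response:** a measure defined before the data are seen and drawn from assessments already planned, namely CT response and the MDT evaluation. Pathological response in resected patients can be a secondary measure.
- **Patients:** all who start chemotherapy and have an evaluable biopsy, with a stated rule for those not resected or not restaged.

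Otherwise, delete the response half from Hypothesis 2, research question 2 and the anticipated outcomes.

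The first option costs a paragraph and one analysis, with no new procedures or patients. Its drawback is precision. The Protocol says "This study aims to recruit approximately 20 patients", and Section 6c allows FAP staining only after diagnostic needs are met and rules out invasive sampling solely for the study, so about 20 is an upper bound. The estimate will be imprecise and should be labelled exploratory. The second option costs only a text edit, but gives up the question.
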